5.2. CONTOURING

Organs

Prostate has to be defined as Clinical target Volume (CTV). Seminal vesicles will be delineated in their proximal part, i.e. 2 cm from their prostate attachment in the cranio- caudal and lateral directions. Rectum is defined 2 cm upper and lower the CTV1. The bladder should be

drawn on each slide where it appears. Femoral heads are defined from the head of the acetabulum to the trochanter.

Planning volumes

CTV1 = prostate + seminal vesicles

CTV2 = prostate

- ARM 1:
 - PTV1 = CTV1 + 1cm (0.5 cm in the posterior direction)
 - PTV2 = CTV2 + 1cm (0.5 cm in the posterior direction)
 - PTV2_{3mm} = CTV2 + 0.3 cm
- ARM 2:
 - PTV1 = PTV2 + [VS+ (1 cm cranial, 1 cm lateral, 0.3 cm anterior and 0.5 cm posterior)]
 - PTV2_{3mm} = CTV2 + 0.3 cm

Dose constraints

ARM 1: IGRT arm with standard margins

PTV2: 95% of the volume covered by the 95% prescription dose (59 Gy).

D 99% \geq 90% of the prescribed dose (55,8 Gy), D 107% \leq 2% of volume,
Dmax (0.1%)<110%

PTV1: 95% of the volume covered by the 95% prescription dose (42 Gy)

Rectum: Dose 0.1% \leq 62 Gy (59 Gy if possible),

V53 Gy \leq 50%

Bladder: D0.1% \leq 63 Gy.

V53 Gy \leq 50%

ARM 2: Calypso® arm with margin reduction

PTV2:

D 99.5% (99% accepted) of the volume \geq 95% prescription dose 59 gy.

V 100 % of the prescribed dose (62 Gy) \geq 90% PTV2

PTV1:

D 99.5% (99% accepted) \geq 95% prescription dose 42 Gy

V 100 % of the prescribed dose (' Gy) \geq 90% PTV1

Rectum: Dose 0.1% \leq 62 Gy (59 Gy if possible), V53 Gy \leq 50%

Bladder: D0.1% \leq 63 Gy. V53 Gy \leq 50%

5.3. DOSE PRESCRIPTION

62 Gy will be delivered to the PTV2 for patients in arm 1 and PTV2 3mm for patients in arm 2, and 44 Gy to the PTV1 for patients in both arms in 20 fractions.

The period treatment will be of 4 weeks.

5.4. BEAM DELIVERY

All treatment will be delivered with Volumetric Modulated Arc therapy using 2 arcs.

5.5. PATIENT SETUP AND VERIFICATION

Arm 1: CBCT and kV-kV positioning + per-fraction verification with kV imaging each 90° of rotation and gating with True Beam V2.0.

Arm 2: CBCT and Calypso positioning + calypso per-treatment tracking.

5.6. CONCOMITANT ANDROGEN DEPRIVATION

Concomitant hormonotherapy using 3 to 6 months Luteinizing Hormone – Releasing Hormone (LH-RH) agonists will be used in intermediate-risk patients unless medical contra- indication, according to the standard practice.

6. Expected Adverse events

Adverse events (AEs) will be assessed according to the NCI-CTCAE v4.03 toxicity scale (see appendix 2).

The most frequent AEs due to the beacon implant are:

- Bleeding (hematuria, hematospermia, hematochezia),
- Pain (procedural, anal, perineal, bowel movements, unspecified),
- Dysuria,
- Infection (urinary tract infection with prostate infection which occur in <2% of patients),
- Fever.

Other observed AEs include:

- Urinary retention,
- Urinary obstructive symptoms (urinary frequency, weak stream, etc.),
- Implant migration.

The following AEs also have been documented following transrectal biopsy; however, they occur in <1% of patients:

- Nausea or sickness
- Allergic reaction to antibiotic prophylaxis
- Perineal swelling
- Sepsis
- Epididymitis
- Temporary fecal incontinence
- Urethral perforation
- Deep venous thrombosis
- Vascular embolization of the implant (pulmonary embolism)
- Vasovagal episode
- Cardiac arrhythmia

Expected acute AEs due to the radiotherapy are:

- Moderate fatigue,
- An increase in the frequency of urination and defecation,
- Rectal burning sensation with sometimes hemorrhoids crisis,
- Increased frequency to defecate without excretion of stools.

Expected late AEs due to the radiotherapy are:

- Difficulty to urinate,
- An increase in the frequency of urination and defecation,
- Rectal or bladder bleeding
- Sexual difficulties.

The decision to discontinue radiotherapy due to unacceptable toxicity will be taken in agreement with the coordinator and the investigator.

7. Study plan and timing procedures

7.1. FLOW CHART OF THE STUDY

	Baseline	Before radiotherapy	During Radiotherapy	End of radiotherapy	Follow-up (from end of radiotherapy)								
					M1	M3	M6	M12	M18	M24	M36	M48	M60
Signed informed consent form ¹	+												
Review of eligibility criteria	+												
Demographic information	+												
Medical, surgical and oncologic history ²	+												
Height ³ , Weight	+												
ECOG performance status	+												
Clinical examination	+			+	+	+	+	+	+	+	+	+	+
Toxicity evaluation (CTCAE V4.03)	+	+ ⁴	+	+	+	+	+	+	+	+	+	+	+
Pelvic MRI or AP CT-scan ^{4 5}	+												
Bone scan or whole-body bone MRI ⁶	+												
PSA test	+					+	+	+	+	+	+	+	+
Before randomization	Simulation CT-scan (optional MRI)	+											
After randomization	Arm 1: Conventional IGRT ⁷		+	Conventional positioning									
	Arm 2: Calypso beacon implant ⁸ Simulation CT-scan ⁹		+	Calypso positioning and tracking									
RILA test	-	+											
Quality of life EORTC questionnaires QLQ-C30 and QLQ-PR25 ⁰	+			+	+	+	+	+	+	+	+	+	+
IPPS and IIEF5 questionnaires ¹¹	+			+	+	+	+	+	+	+	+	+	+

¹ **Signed informed consent form:** prior to any study procedures

² **Medical, surgical and oncologic history:** including cancer diagnosis, prior surgery, concurrent illness, concomitant treatment.

³ **Height:** only at baseline.

⁴ **Toxicity evaluation (CTCAE V4.03):** if the patient is randomly assigned to the arm 2 then the toxicity evaluation (including urinary, rectal and sexual symptoms) will be performed before and after the Calypso beacon implant.

^{5, 6} **Pelvic magnetic resonance imaging (MRI) or abdomino-pelvic (AP) CT-scan and Bone scan or whole-body bone MRI** are required for the intermediate clinical stage. **AP CT-scan and Bone scan or whole-body bone MRI** are left at the investigator's discretion for the low-risk clinical stage.

During and after the treatment radiologic procedures are left at the investigator's discretion.

⁷ **Conventional IGRT** if the patient is randomly assigned to the arm 1.

⁸ **Calypso beacon implant** if the patient is randomly assigned to the arm 2.

⁹ **Simulation CT-scan** if the patient is randomly assigned to the arm 2: will be performed 14 to 28 days after the implant for radiotherapy planning.

^{10, 11} **Quality of life evaluation** using questionnaires will be performed before and at the end of treatment and at each evaluation (1 month, 3 months, every 6 months until two years then every year from end of radiotherapy).

¹¹ **International Prostate Symptom Score (IPSS) and International Index of Erectile Function (IIEF5).**

7.2. CLINICAL EVALUATION AND FOLLOW-UP PROCEDURES

7.2.1. BASELINE

The following procedures and assessments will be performed before any treatment:
The patient must provide a signed informed consent form prior to any study related procedures.

- Review of eligibility criteria (medical, surgical and cancer histories),
- Demographic information,
- Medical, surgical and oncologic history including cancer diagnosis, prior surgery, concurrent illness, concomitant treatment:
 - o Concurrent illness: diabetes*,
 - o indication for hormonotherapy*,
 - o Anticoagulant treatment*,
- Height, weight,
- ECOG performance status (appendix 1),
- Clinical examination,
- Toxicity evaluation,
- Pelvic MRI or AP CT-Scan within 4 months prior to starting treatment,
- Bone scan or whole-body bone MRI within 4 months prior to starting treatment,
- PSA test,
- RILA test (see paragraph 9)*,
- Quality of life using QLQ-C30 (appendix 10) and QLQ-PR25 (appendix 11) questionnaires [42],
- IPPS (appendix 12) and IIEF5 (appendix 13) questionnaires [43].

* Those procedures are required for randomization.

The RILA test will be performed during the first consultation or at the time of simulation CT-scan visit and after signed informed consent form.

Before randomization, a simulation CT-scan (optional MRI) will be performed. A consultation with an anesthetist will be planned in order to perform the Calypso beacon implant. According to the randomization result, the consultation will be only performed in the Calypso arm (arm 2) and cancelled in the arm 1.

7.2.2. BEFORE RADIOTHERAPY (AFTER RANDOMIZATION)

- Conventional IGRT protocol if the patient is randomly assigned to the arm 1.
- Calypso beacon implant if the patient is randomly assigned to the arm 2. The toxicity evaluation (including urinary, rectal and sexual symptoms) will be performed before and after the Calypso beacon implant. The information concerning the implant and the patient monitoring will be noted in the medical record. Patients will be instructed to contact the centre in case of any complication after the beacon implantation.

7.2.3. DURING RADIOTHERAPY

Toxicity evaluation will be done.

Toxicities will be assessed every week during radiation period according to the CTCAE V4.03.

7.2.4. END OF RADIOTHERAPY

- Clinical examination,
- Toxicity evaluation (CTCAE V4.03),
- Quality of life using QLQ-C30 and QLQ-PR25 questionnaires,
- IPPS and IIEF5 questionnaires.

7.2.5. FOLLOW-UP PERIOD (1, 3, 6, 12, 18, 24, 36, 48, 60 MONTHS FROM THE END OF RADIOTHERAPY)

- Clinical examination,
- Toxicity evaluation (CTCAE V4.03),
- PSA test,
- Quality of life using QLQ-C30 and QLQ-PR25 questionnaires,
- IPPS and IIEF5 questionnaires.

8. Assessment endpoints

8.1. PRIMARY ENDPOINT

The primary endpoint is defined by the incidence of grade ≥ 2 late pelvic toxicities between 3 months and 2 years after treatment (based on the Common Terminology Criteria for Adverse Events Version 4.03).

8.2. SECONDARY ENDPOINTS

The secondary endpoints include:

- Any acute toxicity (until 3 months post radiotherapy)
- Any late toxicity (between 3 months and 2 years post radiotherapy),
- Biochemical relapse-free survival (BRFS) at 5 years is assessed by PSA tests: PSA nadir + 2*,
- Complication relapse-free survival (CRFS) (at 2 years)* *,
- Complication relapse-free survival (CRFS) (at 5 years)* *,
- Quality of life evaluation using EORTC QLQ-C30 and QLQ-PR25 questionnaires before and at the end of treatment and at each evaluation (1 month, 3 months, every 6 months until two years then every year from end of radiotherapy),
- Specific questionnaires for urinary obstruction (IPSS) and for erectile function (IIEF5) before and at the end of treatment and at each evaluation (1 month, 3 months, every 6 months until two years then every year from end of radiotherapy),
- Correlation between late toxicity (between 3 months and 2 years post radiotherapy) and the radiation-induced T-lymphocyte apoptosis (RILA) rate (low (≤ 15) versus high (> 15)).

BRFS is defined as the interval between the date of randomization and the date of detection of a biochemical failure (definition below), clinical relapse or death, whichever occurs first.

Biochemical failure after radiation therapy is defined as an increase in the PSA value more than the nadir of the PSA + 2 ng/ml.

**CRFS is defined as the interval between the date of randomization and the date of rectal or urinary grade 2 or more late toxicity, biochemical relapse, clinical relapse or death, whichever occurs first

COVID-19 Health crisis, and after reporting data during this period, didn't have an impact on the protocol medical care of patients included in this study and therefore didn't have an impact on the assessment endpoint defined initially.

9. Rila test

The RILA test results will be used for the stratified randomization and for the correlation between the late toxicity and the RILA rates (see appendix 7).

For the RILA test, one 10 ml Lithium Heparin (LiH) blood tube should be collected on Monday or on Tuesday at baseline and before randomization.

Tubes will be identified with the subject's study code, date and time of sampling, and identification number of the investigational site.

The tubes will be then sent to the Institut de Recherche en Cancérologie de Montpellier - INSERM:

[name]- Equipe AP ([contact])
INSERM - U1194- IRCM (EX U896)
Magasin sous-sol du Bât. Recherche F2

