5.1. PATIENT WORKFLOW FOR IMPLANT AND SIMULATION

Patients will undergo Computed Tomography (CT) scan based and Magnetic Resonance Imaging based (optional) virtual simulations before fiducial implants in order to enhance target volume accuracy.

They will then undergo a Calypso beacon implant (arm 2) according to the treatment arm allocation (see appendix 5 for the implantation instructions). The Calypso beacon implant will be performed at the Beau Soleil Clinic Urology Department (Montpellier).

Arm 2: patients will undergo a second CT-scan simulation 14 to 28 days after the implant for radiotherapy planning. The radiotherapy will be performed 3 to 6 weeks after the implantation.

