10.2. STATISTICAL ANALYSIS

A detailed statistical analysis plan (SAP) will be elaborated before the database is frozen. No formal statistical comparison will be made between the treatment arms.

Data will be summarized using frequencies and percentages for categorical variables and using medians and ranges for continuous variables.

The percentage of patients without grade ≥ 2 late pelvic toxicity (P_{obs}) (success) occurring after 3 months and until 2 years after treatment, as well as the percentage of patients experiencing at least a grade ≥ 2 late pelvic toxicity in that period ($1-P_{obs}$; primary endpoint of the trial) will be presented for each arm with their respective 90% (and 95%) confidence interval based on binomial exact distribution.

The decision about the effect of the experimental arm (Calypso system with reduction of treatment margins) in terms of late pelvic toxicity rate will be stated according the decision rules described in previous section (sample size calculation).

Moreover, in order to control for the additional heterogeneity introduced with the switch to moderate hypofractionation RT we will use a meta-analytic approach in order to consider this factor (i.e. the fractionation-group: normofractionned or moderate hypofractionned) into the calculation of a global pooled proportion of success (and its IC95%) in the experimental Calypso arm.

This analysis will be performed using the Metaprop Stata module, implemented to perform meta-analysis of proportions in the Stata software (References are listed here below). A random effect model will be used to calculate a pooled global estimated of the proportion of success. Metaprop also allows computation of 95%CI using the score statistics and the exact binomial method, and incorporates the Freeman-Tukey double arcsine transformation of proportions. I^2 statistic will be used to describe the percentage of total variation due to the inter fractionation-group heterogeneity. All the details concerning this part of the analysis will be also specified in the SAP [44, 45].

Biochemical and complication relapse-free survival curves will be estimated using the Kaplan-Meier method.

The analysis of QLQ C30 and QLQ PR25 questionnaires will be performed in accordance with the EORTC guidelines.

Specific questionnaires for urinary obstruction (IPSS) and erectile function (IIEF5) will be described at each evaluation and over time.

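### BRFS and CRFS are timed from randomisation but follow-up visits from the end of radiotherapy, so the 5-year BRFS omits failures first found at M60

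*Combined protocol and SAP*

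**What the plan says.** Section 8.2 defines both time-to-event endpoints from randomisation: "BRFS is defined as the interval between the date of randomization and the date of detection of a biochemical failure", and "CRFS is defined as the interval between the date of randomization and the date of rectal or urinary grade 2 or more late toxicity". Clinical relapse and death are also events in both, and biochemical relapse is a component of CRFS. Fixed reading times are named: "Biochemical relapse-free survival (BRFS) at 5 years is assessed by PSA tests: PSA nadir + 2" and "Complication relapse-free survival (CRFS) (at 2 years"), with CRFS at 5 years listed as well.

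The visit schedule uses another clock. Section 7.2.5 is headed "FOLLOW-UP PERIOD (1, 3, 6, 12, 18, 24, 36, 48, 60 MONTHS FROM THE END OF RADIOTHERAPY"), and the flow chart in section 7.1 counts follow-up from the same point. The primary endpoint (section 8.1) also runs from treatment, from 3 months to 2 years afterwards.

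Randomisation precedes treatment (section 4.3). In Arm 2 an implant follows, and "The radiotherapy will be performed 3 to 6 weeks after the implantation" (section 5.1). Radiotherapy takes 4 weeks (section 5.3), while earlier patients received 40 fractions (section 1.1).

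On analysis, section 10.2 says only that "Biochemical and complication relapse-free survival curves will be estimated using the Kaplan-Meier method". It gives no visit window, no rule for the reading time and no interval-censoring method, and it leaves detail to a SAP to be written before the database is frozen.

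**The concern.** A biochemical failure first found at M60 is dated at the M60 visit. On the randomisation clock that is later than 60 months, so it is not counted in a Kaplan-Meier value read at 60 months. The last scheduled PSA that can contribute is M48. The rate would be labelled 5-year but would rest on 48 months of scheduled PSA, and the error always makes control look better.

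Section 1.4 expects less toxicity with no loss of efficacy, and section 1.3 presents equal efficacy as a question to settle before the technique is widely adopted. With reduced margins, biochemical control is the main evidence on that question. There is also an inconsistency within the report: 2 years in CRFS covers a shorter period after radiotherapy than 2 years in the primary endpoint.

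**Working it through.** **Plan's own figure.** The documents give no expected rate, precision or power for BRFS or CRFS, so there is nothing to reproduce for these endpoints. The primary design does reproduce: ((1.645·√(0.85·0.15) + 1.282·√(0.95·0.05))/0.10)² = 75.1 against the stated 75. It does not enter this point.

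**Step 1: delay from randomisation to end of radiotherapy.** Inputs are implant to radiotherapy 3 to 6 weeks (section 5.1), 20 fractions in 4 weeks (section 5.3), and 40 fractions for earlier patients (section 1.1), taken as 8 weeks on the assumption of 5 fractions per week. The wait from randomisation to implant (Arm 2) or to the start of radiotherapy (Arm 1) is not stated and is set to zero, so these are minimum delays. Months = weeks × 7/30.4375.

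| Group | Weeks | Months | M24 at | M60 at |
|---|---|---|---|---|
| Arm 1, 20 fractions | 4 | 0.9 | 24.9 | 60.9 |
| Arm 1, 40 fractions | 8 | 1.8 | 25.8 | 61.8 |
| Arm 2, 20 fractions | 3–6 + 4 = 7–10 | 1.6–2.3 | 25.6–26.3 | 61.6–62.3 |
| Arm 2, 40 fractions | 3–6 + 8 = 11–14 | 2.5–3.2 | 26.5–27.2 | 62.5–63.2 |

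If visits are held at their nominal times, M24 and M60 fall after 24 and 60 months from randomisation in every group. The last scheduled visits before those readings are M18 and M48.

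**Step 2: BRFS at 5 years.** Assume a constant hazard λ from the end of radiotherapy, full attendance, and failures found only at scheduled visits. If F is the cumulative failure at 60 months after radiotherapy, λ = −ln(1 − F)/60 and the reported failure is 1 − exp(−48λ) = 1 − (1 − F)^0.8.

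- F = 5%: reported 4.0%, shortfall 1.0 point
- F = 10%: reported 8.1%, shortfall 1.9 points
- F = 15%: reported 12.2%, shortfall 2.8 points

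Part of this shortfall is only the difference between 60 months after radiotherapy and 60 months after randomisation. The endpoint as the protocol defines it has a true value of 1 − exp(−λ(60 − offset)). For F = 10% and offsets of 0.9 to 3.2 months this is 9.9% to 9.5%. Against it, the reported 8.1% is low by about 1.8 to 1.4 points.

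**Step 3: biochemical part of CRFS.** At 5 years the result is as in step 2. At 2 years the last visit is M18, so the reported failure is 1 − (1 − F)^0.75, with F now at 24 months after radiotherapy: 5%, 10% and 15% become 3.8%, 7.6% and 11.5%.

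**Step 4: toxicity part of CRFS at 2 years.** Section 8.2 refers to the date of the toxicity, not of its detection, and section 12.1.2 requires an onset date for every adverse event. With onset dating, only the offset is lost. If late toxicities are spread evenly over months 3 to 24 (21 months), that is 0.9/21 = 4% to 3.2/21 = 15% of them. Only if toxicity were dated at visits would the whole M18 to M24 interval be lost: 6/21 = 29%.

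**The case against.** **Randomisation is a legitimate origin.** It fits the intention-to-treat population in section 10.3, which includes men never irradiated. That stands. The defect lies in pairing that origin with readings at exactly 24 and 60 months and with detection dating.

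**The rates are assumed and only partly visit-detected.** The documents give no failure rate. Deaths, clinical relapses and failures found at unscheduled tests keep their own dates. The step 2 figures are therefore an upper illustration for a purely visit-detected endpoint.

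**No decision depends on it.** Both endpoints are secondary, without a threshold. A 1.9-point shift on 10% is about 0.019 × 83 = 1.6 men in the Calypso arm, against a simple 95% half-width of 1.96·√(0.10·0.90/83) = 6.5 points. This limits the consequence. The shift is nonetheless systematic and avoidable.

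**Curves are planned, so M60 failures appear as later steps.** They do, but section 8.2 names 2- and 5-year rates, and those are what will be quoted.

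Three stronger readings are tempting and not supported:

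- A reader might infer that all PSA and toxicity assessments run from the end of radiotherapy. Baseline and peri-implant assessments do not, and "Toxicities will be assessed every week during radiation period according to the CTCAE V4.03". Only the follow-up visits do.
- A reader might infer that 2-year CRFS misses 29% of late toxicities. That requires visit dating, which the documents do not state, and onset dates are recorded.
- A reader might infer that the longer delay in Arm 2 biases the arms against each other. For visit-detected PSA failure, every man on schedule contributes visits through M48 and not M60, whatever his arm or fractionation. Only deaths, clinical relapses and onset-dated toxicity see the difference in offset, and section 10.2 rules out a formal comparison between arms.

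**Conclusion.** The point holds for BRFS and for the biochemical part of CRFS. Followed as written, the plan gives a 5-year BRFS whose scheduled PSA data stop at M48, and the error favours the treatment. For 10% failure at 5 years after radiotherapy, about 8.1% would be reported. The shortfall is 1.9 points on that clock, or 1.4 to 1.8 points against the true rate at 60 months from randomisation. For the toxicity part of CRFS the loss is about 4 to 15% of late toxicities if dated by onset. The plan should say that onset is the rule.

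The direction follows from the documents, provided visits occur near their nominal times; a visit held early by more than the offset could fall before the reading time. The size rests on a constant hazard, full attendance, purely visit-detected failure, 5 fractions per week for the 40-fraction schedule, and no wait between randomisation and implant or radiotherapy. Any such wait widens the gap between the clocks. The primary endpoint has its own clock and is not affected.

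**What to change.** In section 8.2 and the SAP:

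1. Keep randomisation as the origin for the intention-to-treat analysis. Report the 2- and 5-year rates at a time on that clock that includes the M24 and M60 visits: about 27–28 and 63–64 months from the stated intervals, later if the wait from randomisation to implant or radiotherapy is material. Alternatively, use an interval-censored estimator.
2. If Kaplan-Meier is kept for the 5-year rate, state how men event-free at M60 are handled. M60 is the last scheduled visit, so censoring each man on his own M60 date shrinks the risk set while other M60 results are still due, which inflates the last steps. The interval-censored estimator avoids this.
3. Date CRFS toxicity by the recorded onset of the adverse event.
4. Add a sensitivity curve timed from the end of radiotherapy, to match the primary endpoint's clock.

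The cost is wording and one extra curve, with no new data or visits. The reported rates will be slightly less favourable.
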